7.1 Investigational therapy

[figure not shown]
Screening consents will be signed prior to autologous HCT to access pre-HCT stem cell graft, bone marrow and peripheral blood samples for the correlative studies. Patients will be enrolled after autologous HCT. Patients will be initiated on panobinostat maintenance therapy between day +90 and +180 after autologous HCT. Patients who develop disease progression before day +90 after autologous HCT will be ineligible for the study.

Panobinostat (also known as LBH589) will be provided by Novartis. Oral panobinostat will be supplied as 5-mg, 10-mg, 15-mg or 20-mg pink/opaque-colored, hard gelatin capsules.

Medication labels will comply with US legal requirements and be printed in English. They will supply no information about the patient. The storage conditions for study drug will be described on the medication label.

During the study, panobinostat will be administered orally as either (1) once daily dose of 20 mg (1 x 20-mg capsule) three times per week, every other week, of a 28-day schedule (Cohort A), or (2) once daily dose of 10 mg (1 x 10-mg capsule) daily x 7 days, every other week, of a 28-day schedule (Cohort B). Both cohorts will receive a maximum of 12 cycles of maintenance therapy (Figure 7-1).

Figure 7-1. Panobinostat maintenance schedule

Patients should be instructed to take their once-a-day oral dose of panobinostat at the same time each morning. Each dose of panobinostat should be taken with an 8 oz / 240 ml glass of water. Patients should be instructed to swallow the capsules whole and not chew them. Patients must avoid grapefruit or grapefruit juice and seville (sour) oranges during the entire study.

If a subject experiences toxicity, the dose of panobinostat will be reduced to one level lower (Table 7-1) and maintained at this level for all subsequent cycles unless further toxicities occur. Panobinostat dose modifications will be made according to the toxicity grading. Once a subject's dose of panobinostat is reduced, then that dose will be the maximal dose administered.

On the days of ECG monitoring, drug administration should be supervised by study center personnel and administration time should be recorded.

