7.4.3 Dose modifications for prolonged QTc

All cardiac events should be treated as per the local standard of care and referred to a cardiologist if clinically indicated. The localized readings of ECGs will use the Fridericia correction for QTc interval assessment: QTcF. Any final decisions concerning dose modifications or permanently discontinuing the patient from study drug due to QTcF prolongation will be based on the Investigator's clinical assessment. Any plan to deviate from these guidelines must be previously discussed and agreed upon with Novartis.

Patients must have QTcF < 470 msec to be eligible for the trial. If QTcF is \geq 470 msec or above 60 msec from baseline on a screening or pre-dose ECG, correct any electrolyte abnormalities (hypokalemia, hypomagnesemia, hypocalcemia), and conduct triplicate ECGs (5 minutes apart) and calculate average QTcF. If the average QTcF from the triplicate ECGs remains \geq 470 ms, patient must not be dosed. Pre-dose ECG monitoring is mandatory on days 1 and 5 of cycle 1, and day 1 of cycles 2 through 4. Post dose ECG (3 hours (\pm 15 minutes) post dosing) is mandatory only on days 1 and 5 of cycle 1.

If a screening, pre-dose, or post-dose ECG shows a QTcF \geq 500 ms, patient is not eligible for further treatment. If any of these mandatory ECGs show QTcF \geq 470 msec or 60 msec above baseline, dosing should be held and the above specified measures including follow-up triplicate ECGs and correction of electrolyte abnormalities should be performed. If QTcF abnormality resolves, patients should resume treatment and have QTcF checked pre-dose on day 1 of each cycle for at least the next 3 subsequent cycles. Additional QTcF monitoring should be performed if clinically indicated. If a patient cannot be dosed due to prolonged QTcF for more than 7 days since last dose, patient must be discontinued from study treatment.

Table 7-3 Dose Reductions for QTc Prolongation

Time Point	Average QTcF*	Action
Screening and pre-dose cycle 1 day 1	\geq 470 msec	Delay treatment Correct any electrolyte abnormal values ** and repeat ECG, if the average QTcF \geq 470 msec, do not dose
	Above 500 msec	Patient is not eligible

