Pre-dose cycle 1 day 5 Pre-dose day 1 of subsequent cycles	\geq 470 msec or above 60 msec from baseline for any pre-dose ECG after the patient has commenced treatment***	Omit dose If unresolved within 7 days, discontinue treatment If resolved within 7 days, resume treatment at prior dose for initial occurrence or at reduced dose if recurrent
	Above 500 msec	Permanently discontinue treatment
*QTcF: Heart rate corrected QT interval using the Fredericia formula: $QTc = QT/RR^{0.33}$ **: serum potassium, magnesium, calcium, ***If a single pre-dose QTcF is \geq 470 msec or 60 msec from baseline, subsequent ECGs should be performed in triplicate		

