7.4.5 Follow-up for toxicities

Patients whose treatment is interrupted or permanently discontinued due to an adverse event or abnormal laboratory value must be followed until resolution or stabilization of the event, whichever comes first.

If a patient requires a dose delay of > 28 days from the intended day of the next scheduled dose, then the patient must be discontinued from the study. If however the patient was clearly benefiting from panobinostat therapy, the patient may be able to continue treatment with a dose reduction at the Investigator discretion, after resolution of the adverse event. All patients will be followed for adverse events and serious adverse events for at least 4 weeks following the last dose of oral panobinostat.

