8.1 Visit schedule

Table 8-1 Evaluation and visit schedule

	Pre-HCT (Screening, not required)	Prior to maintenance (Enrollment: +45 to +180) [§]	Cycle #1 (start between +90 and +180)	Cycle #2****	Cycle #3****	Cycle #4****	Cycle #5****	Cycle #6****	Cycle #7****	Cycle #8****	Cycle #9****	Cycle #10*** *	Cycle #11*** *	Cycle #12*** *	End of study visit (4 weeks (± 14 days) follow up after the first dose of cycle #12)
Consent	X ⁺	X													
Enrollment		X													
H&P (SOC)		X	X ^{SS§}	X	X	X	X	X	X	X	X	X	X	X	X
Concomitant medications		X													
Toxicity (adverse event (AE)) assessment ^{SS}			X	X	X	X	X	X	X	X	X	X	X	X	X
Vital signs (SOC)		X ⁺⁺	X	X	X	X	X	X	X	X	X	X	X	X	X
EKG		X	X [*]	X ^{**}	X ^{**}	X ^{**}									
CBC and CMP (SOC)		X	X ^{***}	X ^{***}	X	X	X	X	X	X	X	X	X	X	X
PT/INR/PTT		X			X			X							X
LDH, cholesterol panel, GGT, uric acid		X													
Urinalysis		X													X
TSH, free T4		X													X
Serum pregnancy test ⁺⁺⁺		X	X	X	X	X	X	X	X	X	X	X	X	X	
SPEP, UPEP and serum free		X			X			X			X			X	

Confidential

light chains (SOC)															
Pneumococcal-13 conjugate vaccine (at around day +90 – SOC)		X [#]													
Peripheral blood research samples	X	X	X ^{****}	X	X			X			X				X
Bone marrow research samples	X [@]	X													X
Stem cell graft research samples	X														

*Single 12 lead EKG will be performed for pre-dose and 3 hours (± 15 minutes) post-dose on days 1 and 5 of cycle 1. A total of 4 EKGs during cycle 1 will be performed.
 **Single 12 lead EKG will be performed for pre-dose on day 1 of cycle 2 and beyond at each cycle (at least through cycle 4). If no significant QTcF prolongation is noted during the first cycle, then QTc monitoring is no longer required beyond cycle 4 (and may be performed at the investigator’s discretion). One EKG per cycle from cycle 2 to 4 (minimum).
 ***CBC to be performed weekly during cycle #1 and #2. CBC/CMP will also be performed on day 5 of cycle 1.
 ****Window to start cycles #2 to #12 would be ±7 days from the planned first day of each cycle.
 + Screening consent for research samples (bone marrow, peripheral blood and stem cell graft)
 ++ Height will be measured at screening visit prior to starting panobinostat maintenance therapy
 +++ Only for women of child bearing potential
 ++++ Peripheral blood research samples will be also collected on day 5 of cycle 1.

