8.3.6 ECG

A screening 12-lead ECG will be performed to assess study eligibility. Additional 12-lead ECGs will be performed at a minimum at scheduled time points as indicated in Table 8-2. Pre-dose ECG monitoring is required for the first four cycles of treatment. Post-dose ECGs will be required during cycle one, on days 1 and 5. Additional ECG monitoring should be done at the discretion of the Investigator, as clinically indicated. All ECGs will be read locally.

Table 8-2 Cardiac assessment monitoring schedule

Cycle	Day of cycle	ECG monitoring ^a
	Screening ^b	Single ECG to assess eligibility
Cycle 1	1, 5	Pre-dose: Single 12 lead ECG
	1, 5	3 hours (± 15 minutes) post dose: Single 12 lead ECG
Cycle 2 and beyond	1	Pre-dose: Single 12 lead ECG
^a Refer to Table 7-3 for the recommended dose modifications due to QTc interval prolongation ^b The screening ECGs will be analyzed locally to assess eligibility of the patient. (Note: the mean QTc interval at baseline must be ≤ 470 msec for the patient to be eligible for participation in the trial) Note: If no significant QTcF prolongation is noted during the first 4 cycles, the QTc monitoring is no longer required and may be performed at the Investigator’s discretion, if medically indicated.		

All cardiac events should be treated as per the local standard of care and referred to a specialist if clinically indicated. The localized readings of ECGs will use the Fridericia correction with MUSE system: QTcF. Any final decisions concerning dose modifications or permanently discontinuing the patient from study drug due to QTcF prolongation will be based on the assessment performed by the Investigators using QTcF correction derived from MUSE system. Any plan to deviate from these guidelines should be previously discussed and

agreed upon with Novartis. If a patient cannot be dosed due to prolonged QTcF for more than 7 days since last dose, patient should be discontinued from study.

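### The 7-day QTcF stop in 7.4.3 and 8.3.6 is worded from the last dose, so it has already run out on an on-time day 1 of cycle 2 or later, where Table 7-3 allows 7 days to resolve and resume

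*Combined protocol and SAP*

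**What the plan says.** All references are to the combined protocol and SAP.

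- **7.4.3, text.** If a patient "cannot be dosed due to prolonged QTcF for more than 7 days since last dose, patient must be discontinued from study treatment". Earlier in the same paragraph: "If QTcF abnormality resolves, patients should resume treatment".
- **8.3.6.** The same count with a weaker verb and a different object: "7 days since last dose, patient should be discontinued from study". Footnote a of Table 8-2, in this section, sends the reader to Table 7-3 for QTc dose modifications.
- **Table 7-3, row for pre-dose cycle 1 day 5 and pre-dose day 1 of later cycles.** At the hold threshold (470 msec or more, or over 60 msec above baseline) the dose is omitted. Treatment stops if this is unresolved within 7 days. Otherwise: "If resolved within 7 days, resume treatment at prior dose for initial occurrence". The table does not say when its 7 days begin.
- **7.4.3, ECG days.** "Pre-dose ECG monitoring is mandatory on days 1 and 5 of cycle 1, and day 1 of cycles 2 through 4".
- **7.1, schedule.** Cohort B takes 10 mg "daily x 7 days, every other week, of a 28-day schedule". Cohort A takes 20 mg three times a week on the same alternating weeks.
- **Table 8-1 footnote.** "Window to start cycles #2 to #12 would be ±7 days from the planned first day of each cycle".

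**The concern.** The text and the table deal with the same ECG and appear to start the clock at different times. The text starts it at the last dose taken. The table, in its natural sense, starts it at the dose omitted. With continuous dosing the difference would be small. Here every day 1 after cycle 1 follows a drug-free week, and that week alone uses up the text's allowance.

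The stake is the primary endpoint. Section 13.1.3 reports the proportion completing 12 cycles in 15 evaluable patients per cohort, and 13.1 does not replace patients who leave for toxicity. Section 13.1 counts completion whatever the dose modifications, but a discontinuation is not a dose modification. A patient taken off drug by the wording, whom the table would have let resume, would be counted as not tolerating the regimen.

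**Working it through.** **Inputs.** Cohort A: 20 mg, three doses in each on-week. Cohort B: 10 mg daily for 7 days in each on-week. Both: 28-day cycle, alternate weeks (7.1). Start window for cycles 2 to 12: 7 days either side (Table 8-1). Half-life about 15 hours (2.1.4). Cohort size 15 (13.1).

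**Check on the schedule as read.** Section 3 states 60 mg and 70 mg per week. 3 × 20 = 60 and 7 × 10 = 70, so the reading is right. On-weeks are weeks 1 and 3; weeks 2 and 4 are drug-free.

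**Assumption.** The text does not give Cohort A's dosing days. Days 15, 17 and 19 are assumed for week 3. Over all three-day patterns within days 15 to 21 the last dose falls between day 17 and day 21.

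**Clock.** On-time day 1 of the next cycle is day 29. Days since last dose = start day − last dose day. Days left under the text = 7 − that gap.

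| | Cohort B | Cohort A (15/17/19 assumed) |
|---|---|---|
| Last dose | day 21 | day 19 |
| Limit under the text | 21 + 7 = day 28 | 19 + 7 = day 26 |
| Gap on day 29 | 29 − 21 = 8 | 29 − 19 = 10 |
| Days left, on-time start | 7 − 8 = −1 | 7 − 10 = −3 |
| Days left, earliest start (29 − 7 = day 22) | 7 − 1 = 6 | 7 − 3 = 4 |
| Days left under Table 7-3, if counted from the omitted dose | 7 | 7 |

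For any Cohort A pattern the on-time gap is 29 − 21 = 8 to 29 − 17 = 12 days, so it always exceeds 7. Cohort B at dose level −1 (Table 7-1) still doses on the seventh day of the on-week, so its gap stays 8. The text leaves no negative balance only if the cycle starts at least 1 day early (B) or 3 days early (A). Even the earliest permitted start leaves fewer than 7 days.

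**Where it applies.** Four pre-dose ECGs are mandatory after the first dose: cycle 1 day 5 and day 1 of cycles 2, 3 and 4. Three of the four fall after a drug-free week. On cycle 1 day 5 the difference is small. The text's limit is 4 + 7 = day 11 (B) or 3 + 7 = day 10 (A, assumed), against 5 + 7 = day 12 from the omitted dose.

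**When the outcomes differ.** On an on-time day 1 the two rules give different results only if QTcF is confirmed at the hold threshold, is below 500 msec, does not resolve at that visit, and does resolve within 7 days. The endpoint changes only if the patient would otherwise have completed 12 cycles.

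**Size.** One patient is 1/15 = 6.7 points. For example, 10/15 is the hypothesised two-thirds and 9/15 is 60%, the completion level at which 13.1.5 suspends accrual (it does not say whether per cohort).

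**How likely.** The documents give no rate for day 1. Time since last dose is 192/15 = 12.8 half-lives at 8 days and 240/15 = 16.0 at 10 days, which points to rarity, although 2.1.5.1 raises a possible delayed effect. Section 2.1.5 reports, for the every-other-week schedule, increases over 60 msec in 4 patients (4.2%), values over 480 to 500 msec in 1 (1.0%), and none above 500. For 20 mg three times a week every week, Table 2-3 gives 7/309 (2.3%) and 5/309 (1.6%) for the first two.

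**The case against.** The strongest reply is that the sentence carries a qualifier. The patient must be undosable because of QTcF for more than 7 days. In week 4 the patient is off drug because of the schedule, so on an on-time day 1 no time at all has been lost to QTcF. Read that way, text and table agree. The resume sentence in 7.4.3 supports this, since the other reading leaves it almost nothing to do on day 1 of later cycles. So does the Table 8-2 footnote, by which 8.3.6 defers to Table 7-3. Final QTcF decisions also rest with the investigator.

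Much of this stands. The lenient reading is available and is probably the intended one. It does not settle the wording, because the sentence names the last dose as its starting point. Elsewhere the protocol states its starting points explicitly: Table 7-2 counts from the suspension of drug, and 7.4.5 counts a general delay "from the intended day of the next scheduled dose". Investigator discretion does not say which clock is the guideline, and 7.4.3 requires planned departures to be agreed with the supporting company beforehand.

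A reader might infer that the protocol forces every patient with a hold-level QTcF on day 1 off treatment, or that the completion rate will be materially lowered. The documents support neither. Table 7-3 instructs otherwise for that ECG, a hold that clears at the visit is not affected, and the reported QTcF figures suggest few triggers. Those figures are not bounds: Table 2-3 counts worst post-baseline values, monitoring included post-dose ECGs, and the band from 470 to 480 msec cannot be separated out.

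**Conclusion.** The inconsistency is real and of low priority. On its plain words, a mandatory stopping sentence has expired before an on-time day 1 ECG in cycles 2 and later: by 1 day in Cohort B, and by 3 days in Cohort A if dosed on days 15, 17 and 19. The table for the same ECG allows 7 days and resumes only if QTcF has resolved. The Cohort B figure and the minimum 8-day gap in Cohort A follow from the schedule alone. The Cohort A figures of 10 and 3 days rest on the assumed dosing days, and the table's 7 days rest on counting from the omitted dose. No frequency is claimed. The consequence is at most one non-completion, 6.7 points of a 15-patient cohort, per affected patient, in a descriptive proportion whose planned 95% interval widths run from 0.356 to 0.522.

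**What to change.** In both 7.4.3 and 8.3.6, replace the clause that counts from the last dose with: *for more than 7 days after the scheduled dose omitted for prolonged QTcF*. State the same starting point in Table 7-3. Use one consequence in both sections, that the patient must be discontinued from study treatment, so that 8.3.6 no longer has the weaker verb or refers to leaving the study. Keep permanent discontinuation at 500 msec, and keep resumption conditional on a resolved QTcF.

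The cost is one amendment touching two sentences and one table row. It adds no patients or visits, and no ECGs beyond those Table 7-3 already implies. The downside is a longer possible gap. A patient held on day 29 could resume as late as day 36, which is 36 − 21 = 15 days after the last dose in Cohort B and 36 − 19 = 17 in Cohort A (dosing days assumed). The cycle-start window already allows the same gap, with no QTcF event, when a cycle begins 7 days late.

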7.4.4 Study drug discontinuation

It will be documented whether or not each patient completed the clinical study. If for any patient either study treatment or observations were discontinued, the reason will be recorded.

Reasons that a patient may discontinue treatment are considered to constitute one of the following:

1. Disease progression
2. Adverse event(s) related to the study drug
3. Abnormal laboratory value(s) related to the study drug
4. Abnormal test procedure result(s) related to the study drug
5. Protocol violation
6. Subject withdrew consent
7. Lost to follow-up
8. Administrative problems
9. New cancer therapy
10. Death

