7.3 Treatment cycle and duration

One treatment cycle consists of oral panobinostat either (1) 20 mg PO three times per week, every other week, of a 28-day schedule, or (2) 10 mg PO daily x 7 days, every other week, of a 28-day schedule. Patients may continue treatment with oral panobinostat until they experience unacceptable toxicity that precludes further treatment, disease progression, and/or at the discretion of the investigator. The planned treatment is for a total of 12 cycles (48 weeks).

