8.3.1 Adverse events

Information about unexpected grades ≥ 3 adverse events, whether volunteered by the subject, discovered by investigator questioning, or detected through physical examination, laboratory test or other means, will be collected and recorded and followed as appropriate.

An adverse event is the appearance or worsening of any undesirable sign, symptom, or medical condition occurring after starting the study drug even if the event is not considered to be related to study drug. Medical conditions/diseases present before starting study drug are only considered adverse events if they worsen after starting study drug. Abnormal laboratory values or test results constitute adverse events only if they induce clinical signs or symptoms, are considered clinically significant, or require therapy.

The occurrence of adverse events should be sought by non-directive questioning of the patient at each visit during the study. Adverse events also may be detected when they are volunteered by the patient during or between visits or through physical examination, laboratory test, or other assessments. As far as possible, each adverse event should be evaluated to determine:

1. the severity grade (moderate, severe) or (grade 3-4) – only grades adverse events will be reported its relationship to the study drug(s) (suspected/not suspected)
2. its duration (start and end dates or if continuing at final exam)
3. action taken (no action taken; study drug dosage adjusted/temporarily interrupted; study drug permanently discontinued due to this adverse event; concomitant medication taken; non-drug therapy given; hospitalization/prolonged hospitalization)
4. whether it constitutes a serious adverse event (SAE)

All adverse events should be treated appropriately. Such treatment may include changes in study drug treatment including possible interruption or discontinuation, starting or stopping concomitant treatments, changes in the frequency or nature of assessments, hospitalization, or

any other medically required intervention. Once an adverse event is detected, it should be followed until its resolution, and assessment should be made at each visit (or more frequently, if necessary) of any changes in severity, the suspected relationship to the study drug, the interventions required to treat it, and the outcome.

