13.1 Statistical methods and data analysis

This is an open label study of 2 different panobinostat maintenance dosing schedules after autologous HCT in patients with multiple myeloma. There are 2 cohorts and patients will be enrolled sequentially to cohort A, then to cohort B. The sample size is 30 patients for this trial (15 for each cohort). We expect that at least 2/3 of each cohort will complete 12 cycles of maintenance panobinostat (regardless of dose modification) and will be evaluable for the primary endpoint. The widths of 95% confidence interval (CI) are 0.356, 0.438, 0.487, 0.514, and 0.522 when the proportions of patients tolerating 12 cycles of maintenance are 0.9, 0.8, 0.7, 0.6, and 0.5, respectively.

A patient who withdraws from the study due to reasons other than death, disease progression or toxicity will be replaced and is considered as non-evaluable for primary endpoint. The proportion of patients tolerating the therapy will be reported with 95% CI. All 30 patients are eligible for secondary endpoints. We will compute the overall response rates before the transplant, after autologous HCT, and after the completion of maintenance therapy, and at best response. The OS and PFS will be estimated using the Kaplan-Meier method. We will also report the incidences of all grades and grade ≥ 3 toxicities. The two-sided 95% CIs for

proportion, and OS and PFS will be computed using the Clopper-Pearson method and the Greenwood formula, respectively. In addition, the frequency of B cell precursor as well as other cell subsets, and their 95% CI will be evaluated using t-distribution. If data do not meet normality assumption, the power transformation (e.g., log-transformation) will be conducted. Those patients who are not in CR before the transplant would be most suitable for T-effector activity analysis. This will be examined by the paired t-test or the Wilcoxon signed-rank test, depending on the data distribution.

Relative dose intensity (RDI) represents the ratio of the amount of a drug actually delivered [actual dose intensity (DI)] to the amount planned (planned DI). The purpose of calculating RDI is to evaluate whether the planned DI of a chemotherapy treatment was actually achieved which may suggest the feasibility of planned treatment regimen. There are multitude of reports demonstrating a correlation between RDI and survival in cancer treatment.

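### Stop-reason codes require drug-relatedness and 'toxicity' is undefined, so an early stop for an unrelated adverse event or by investigator decision can be replaced and leave the completion-rate denominator

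*Combined protocol and SAP*

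**What the plan says.** Section 7.4.4 introduces its list with "Reasons that a patient may discontinue treatment are considered to constitute one of the following" and gives ten entries. Three concern tolerability: "Adverse event(s) related to the study drug", "Abnormal laboratory value(s) related to the study drug" and "Abnormal test procedure result(s) related to the study drug". There is no entry for an adverse event judged unrelated, for an investigator's decision, or for any other reason.

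Other sections allow stops that this list cannot hold. Section 7.3 lets treatment end on unacceptable toxicity, "disease progression, and/or at the discretion of the investigator". Section 7.4.5 refers to permanent discontinuation for an adverse event or abnormal laboratory value and sets no attribution condition. Section 8.3.1 counts an event as adverse "even if the event is not considered to be related to study drug".

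Section 13.1 then sets the rule for the primary endpoint: "A patient who withdraws from the study due to reasons other than death, disease progression or toxicity will be replaced". Such a patient is non-evaluable for that endpoint. Section 13.1.3 reports 12-cycle completion in 15 evaluable patients per cohort, against a hypothesis of at least two-thirds. Section 13.1.5 suspends accrual if the completion rate is 60% or less.

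**The concern.** The primary endpoint is the proportion of patients who complete 12 cycles. A patient who stops for an adverse event that the investigator calls unrelated, or because the investigator decides to stop, has no matching code. If the stop is not regarded as toxicity, section 13.1 allows the patient to be replaced and removed from the denominator.

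The relationship judgement is the investigator's and is binary (suspected or not suspected). It is made open label, without randomization or an untreated control, and with the cohort and the early stop already known. Section 5 says it is unknown whether panobinostat's toxicity will be accentuated after transplant, so attribution is hard in exactly this setting. Exclusions of this kind can only raise the reported completion rate. With 15 patients per cohort, one or two are enough to move it visibly.

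**Working it through.** **The plan's own figure.** Section 13.1 gives 95% CI widths of 0.356, 0.438, 0.487, 0.514 and 0.522 for completion proportions of 0.9, 0.8, 0.7, 0.6 and 0.5. The Clopper-Pearson interval with n = 15 and x = 15p (non-integer x allowed) gives 0.3561, 0.4376, 0.4868, 0.5138 and 0.5224. All five agree, so the sample-size figures are not in question.

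**How the word toxicity is used.**
- Section 13.1: the replacement rule uses it without a definition.
- Table 8-1: the assessment row treats toxicity and adverse event as the same thing, and section 8.3.1 defines adverse events regardless of cause.
- Section 7.3: unqualified.
- Section 7.4.2: explicitly limited to toxicity related to the study drug.
- Section 7.4.4: the codes for stopping require relatedness.

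The first usage is open, the next two favour a broad reading, and the last two favour a narrow one.

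**Illustration in one cohort of 15.** Suppose 9 patients complete and k of the 6 early stops are excluded. The rate is 9/(15 − k).

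| k excluded | Rate | 95% CI (Clopper-Pearson) |
|---|---|---|
| 0 | 9/15 = 60.0% | 32.3% to 83.7% |
| 1 | 9/14 = 64.3% | 35.1% to 87.2% |
| 2 | 9/13 = 69.2% | 38.6% to 90.9% |
| 3 | 9/12 = 75.0% | 42.8% to 94.5% |

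**With replacement up to 15 evaluable.** Let c be the completion probability counting every stop, and u the share of patients excluded and replaced. The expected reported rate is c/(1 − u). The documents do not give u, so the values below are assumptions. The last column is the binomial probability of at least 10 completers in 15, the two-thirds level in section 13.1.3.

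| u (assumed) | 0.60/(1 − u) | P(at least 10 of 15) |
|---|---|---|
| 0 | 60.0% | 0.403 |
| 3.3% | 62.0% | 0.468 |
| 6.7% | 64.3% | 0.541 |
| 10% | 66.7% | 0.618 |
| 13.3% | 69.2% | 0.698 |
| 20% | 75.0% | 0.852 |

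At c = 0.50 the same range of u raises this probability from 0.151 to between 0.184 and 0.483.

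**The case against.** The strongest reply is that section 13.1 turns on toxicity, not on the section 7.4.4 codes, and does not add a relatedness condition. Where the protocol means only related events, as in section 7.4.2, it says so. Read with Table 8-1, any adverse-event stop would be toxicity, evaluable and not replaced. This reading is reasonable, and it means that exclusion is not mandated. A reader might infer that the causality call decides evaluability; the text shows only that it can. The broad reading is not stated either, and it does not cover a stop by investigator decision.

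Four further objections stand in part.
- Section 7.4.4 concerns stopping treatment, while section 13.1 concerns withdrawing from the study. A patient who stops the drug but stays in follow-up is not clearly replaceable. Section 7.4.5 blurs the line by discontinuing patients from the study after a delay of more than 28 days, with an investigator exception.
- A reader might infer that unmatched stops must be filed as administrative or as withdrawn consent. The protocol gives no such mapping, and they could equally be called related. That would protect the denominator but distort the attribution record.
- Section 8.3.1 already asks for relationship and for whether the drug was permanently discontinued. But sections 8.3, 8.3.1 and 12.1 limit collection to unexpected grade 3 or higher events and serious events, and a Table 8-1 footnote limits it to grade 3 or higher. A stop for a persistent, non-serious grade 2 event may leave only its stop code.
- The shifts are small beside an interval about 0.51 wide, and two-thirds is a hypothesis, not a decision rule. Relative dose intensity is also reported. However, this shift runs in one direction, and the interval does not allow for it.

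It may also be said that counting unrelated events as failures is an endpoint choice. That is so, but the plan has to make the choice explicitly. Death and progression already escape replacement whatever their cause.

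**Conclusion.** The gap is real and should be closed. A closed code list that requires relatedness, a permitted stop that has no code, and an undefined word in the replacement rule together allow intolerance to leave the primary endpoint.

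The size is unknown. The move from 60% to 69% assumes 9 completers in 15 and 2 excluded stops. The 62% to 75% range assumes c = 0.60, u between 3.3% and 20%, exclusion of every such stop, and replacements who behave like the other patients.

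Two stronger readings are not supported. A reader might infer that the suspension trigger is weakened, since 9/15 meets the 60% limit and 9/13 does not. But section 13.1.5 does not restrict its rate to evaluable patients or say that replaced patients leave it. A reader might also compare 10/15 = 67% after two replacements with 10/17 = 59%. That is not what a no-replacement rule would give, because the cohort would then stop at 15.

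**What to change.** In section 7.4.4, reword reasons 2 to 4 as an adverse event, laboratory abnormality or test abnormality regardless of relationship. Record relationship in a separate field for every such stop, including those below grade 3. Add an investigator-decision entry with the reason specified.

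In section 13.1, state that stopping study drug before 12 cycles counts as non-completion and is not replaced when it is for an adverse event, laboratory abnormality or test abnormality of any attribution, or by investigator decision for a medical reason. State that this holds whether or not the patient stays in follow-up. In section 13.1.5, state that the 60% rate uses the same classification.

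This changes a case-report-form code list and some wording, not any rule on when treatment stops. The reported completion rate may be slightly lower, and some truly unrelated events will count as failures. The relationship field lets these be shown separately.
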